## A Introduction

### A1 Study Abstract

Persons with spinal cord injury (PwSCI) are at a greater risk for major health conditions and poorer health outcomes than persons without spinal cord injury. For PwSCI, habitual exercise is critical for both physiological and psychological well-being. Prior research indicates that exercise programs conducted in a controlled setting have positive effects on the physical and psychosocial fitness of PwSCI, but the efficacy and feasibility of these programs are not well understood in community-based settings. PwSCI will be randomized to a 12-week community-based exercise intervention (CBEI; n = 20) or an exercise education control group (EEG; n = 20). The proposed project aims to examine

---

potential health benefits in response to the intervention and identify the barriers and facilitators to successful implementation of a CBEI in PwSCI (N = 40).

## **A2 Primary Hypothesis**

The community-based exercise group (CBEI) will have a 10% improvement in peak oxygen consumption (VO2peak), upper extremity strength, body fat, cardiovascular risk profile (fasting plasma HDL cholesterol, triglycerides, and insulin resistance), and psychological well-being (sleep, pain, fatigue, and depression) as compared to the exercise education control group (EEG) post-intervention.

## **A3 Purpose of the Study Protocol**

The purpose of the study is to examine the impact of a community-based exercise intervention for persons with spinal cord injury on physiological and psychological well-being and identify barriers and facilitators to implementation.

## **B Background**

### **B1 Prior Literature and Studies**

#### **Background:**

**SCI and exercise:** Approximately 285,000 people in the US are living with an SCI. PwSCI are at a greater risk for heart disease, high blood pressure, obesity, and diabetes than those without disabilities. SCIs often result in various physiological alterations affecting multiple body systems, including blunted hemodynamics, altered sympathetic innervation, altered glycemic control, reduced active muscle mass, deteriorated circulatory vessels below level of injury, and impaired arterial compliance and function. These pathophysiological alterations amplify the risk and prevalence of cardiovascular and metabolic diseases in PwSCI, suggesting a great need for increased physical activity and fitness in this population. The typical daily routine of PwSCI does not stress the cardiorespiratory system enough to produce positive health-related changes; therefore, structured exercise activities are needed to enhance physical capacity and to reduce the likelihood of secondary complications. Increased cardiorespiratory fitness in PwSCI promotes not only improved functional independence, but also improved cardiovascular and metabolic health.

**Exercise recommendations and barriers:** Despite the widely recognized health benefits of regular physical activity, PwSCI report the lowest levels of physical activity compared to other populations, with fewer than 50% engaging in any physical activity, and only 15% engaging in physical activity sufficient to gain meaningful health benefits. The most recent evidence-based exercise guideline for PwSCI recommends engagement in at least 30 minutes of moderate-to-vigorous-intensity aerobic exercise three times per week to achieve cardio-metabolic health benefits. Because of decreased sympathetic innervation, muscle atrophy, and decreased cardiac reserves, it is difficult for PwSCI to achieve these intensity levels without proper support. There is a considerable lack of accessible facilities, equipment, and support for PwSCI outside of rehabilitation, and PwSCI also often lack knowledge of the types of exercise that will allow them to be successful in exercise. Typical exercise facilities (e.g., YMCA, 24 Hour Fitness) generally do not provide the types of support necessary for PwSCI to successfully exercise. More evidence is needed to identify effective exercise

---

interventions implemented outside of the rehabilitation setting that improve health for PwSCI.

**Preliminary Work:** We have conducted two related studies that support this proposed project. The first was a single-arm design that assessed 284 PwD (63 PwSCI) who joined the Paraquad Health and Wellness Center (PQHWC), an accessible gym with equipment and staff to support PwD. Participants were encouraged to work on strength and endurance exercises but were not monitored. We compared participants' weight, BMI, pain, endurance, and strength pre- and post- 12 weeks of participation in the PQHWC. Total group results showed significantly decreased average pain reported over the past 30 days and significant increases in four upper extremity strength exercises ( $p < .05$ ). No changes in body weight, BMI, or endurance were found. Limitations of this study were the lack of control group for comparisons, lack of rigorous assessments to identify changes at the cardiorespiratory or metabolic levels, and lack of structure to adequately meet the physical activity guidelines for PwSCI.

The second study was qualitative and involved interviews of seven active participants in the PQHWC and six staff members, the purpose of which was to gather participant and staff perspectives about the impact of the program and suggestions for evaluation. Participants identified knowledgeable staff, options for adapted exercise equipment, and a positive social environment as critical program components. However, participants reported that although the supports were in place to exercise, their knowledge about how they should exercise was limited. Staff expressed the need for sound measures to identify whether participants were making changes. These two studies identified weaknesses of a community-based exercise program and the need for an exercise intervention that provides structure and education for PwSCI. Through the information learned in these studies, we developed the structured, 12-week CBEI proposed in this application.

## ***B2 Rationale for this Study***

Although a wealth of evidence exists regarding the benefits of exercise interventions for PwSCI, there is limited research on exercise interventions that are community-based and follow the recommended guidelines. Previous studies of community-based exercise programs have varied widely in their populations of focus, research designs, exercise protocols, and health outcomes. Many of these studies lack the rigorous designs, sample sizes, and testing needed to examine the effects of exercise on key health outcomes. As a result, there is extensive variability in evaluation methods among published studies. Additionally, metabolic measures are not often included in studies based in the community. The *proposed research is innovative* because it addresses factors that often impede successful implementation of exercise for PwSCI in the community, follows the recommended guidelines, and uses sound measures.

Cardiorespiratory-related diseases account for approximately 40% of mortality as the leading cause of death for PwSCI. For PwSCI, the decline in physical capacity and increased risk of secondary health conditions often result in reduced independence and participation in life activities. About 30% of PwSCI are re-hospitalized one or more times any given year following injury, with an average length of stay of 22 days. PwSCI who are physically active tend to make fewer visits to physicians and experience fewer medical complications and hospitalizations than their sedentary counterparts. Participating in recommended amounts of exercise may offer an effective method for

---

increasing cardiovascular fitness and metabolic health in PwSCI. Therefore, it is imperative to build supports and resources outside of rehabilitation to promote health and well-being to improve physiological and psychosocial outcomes experienced by PwSCI. The *significance of this project* is its focus on a CBEI that uses accessible equipment and health professionals to implement multi-modal exercise programs that are individualized to each participant's needs and meet recommended guidelines. This study has the potential to establish a community-based model to be emulated in other settings.

## **C Study Objectives**

### **C1 Primary Aim**

**Primary Aim: To estimate improvements in physical function, cardio-metabolic health, and psychological well-being of participants enrolled in a CBEI compared to an education-only control group.**

Forty PwSCI will be randomized into either the CBEI group or the EEG receiving education only. We will measure physical function (cardiorespiratory fitness and strength), cardio-metabolic health (body composition, glucose tolerance, and cardiovascular risk profile), and psychological well-being (PROMIS). We hypothesize that the CBEI will have a 10% improvement in peak oxygen consumption (VO2peak), upper extremity strength, body fat, cardiovascular risk profile (fasting plasma HDL cholesterol, triglycerides, and insulin resistance), and psychological well-being (sleep, pain, fatigue, and depression) as compared to the EEG post-intervention.

### **C2 Secondary Aim**

**Secondary Aim: To identify barriers, facilitators, and reasons for positive determinants for PwSCI to exercise in a community-based setting.**

We will use a mixed methods approach to characterize key implementation outcomes: acceptability, feasibility, and fidelity. Information will be gathered during the intervention using activity monitors, heart rate monitors, and rating scales to identify whether exercise intensity rates were met. Participants will be interviewed for the purposes of comparing the experience of participants who experienced change and those who did not. This information will enable us to determine the degree to which the pilot intervention's success or failure was related to implementation outcomes and to inform the development of a future R01-funded clinical trial. We hypothesize that the intervention will be accepted among PwSCI, feasible to implement, and that delivery of the intervention will adhere to the exercise intervention protocol (fidelity).

### **C3 Rationale for the Selection of Outcome Measures**

The primary outcome variables for this randomized controlled trial (RCT) include: cardiorespiratory fitness (VO2peak and 6-minute push test), pain (Wong-Baker FACES), metabolic health (blood chemistries), body composition (dual-energy x-ray absorptiometry [DXA] scan, height, weight, BMI), vitals (heart rate and blood pressure), and psychosocial well-being (PROMIS-29 Profile). These variables are significantly impacted by physically inactive lifestyles, which are highly common among manual wheelchair users (MWUs) with SCI. MWUs with SCI also exhibit and report values of some of these variables below healthy range, potentially impacting physiological health and psychosocial well-being and overall quality of life. Secondary outcome variables

---

include qualitative perspectives of the research staff delivering the exercise intervention and of participants to assess the feasibility of the intervention protocol.

## **D Investigational Agent**

Not applicable

### **D1 Preclinical Data**

Not applicable

### **D2 Clinical Data to Date**

Not applicable

### **D3 Dose Rationale and Risk/Benefits**

Not applicable

## **E Study Design**

### **E1 Overview or Design Summary**

The proposed project utilizes a mixed-methods approach. An experimental strategy using an RCT (single-blinded) will be used. Forty participants ( $n = 40$ ) will be randomized into the CBEI ( $n = 20$ ) or the EEG ( $n = 20$ ) by a research staff member who will not be involved in either conducting outcome assessments or implementation of the intervention. This design will assist in reducing variability and maximizing the effect size for powering a subsequent larger RCT.

The intervention for participants in the CBEI will consist of one-on-one, formally directed exercise sessions by trained staff in the PQHWC. The CBEI is based on the recent evidence-based exercise guideline for PwSCI, American College of Sports Medicine's (ACSM) Physical Activity Recommendations for PwSCI, best available evidence, and preliminary work. The intervention will include 36 60–90-minute sessions over 12 weeks (three sessions/week) with a goal of participants guiding their own exercise regimens by the end of the intervention. Personalized exercise sessions will be created for each participant based on fitness goal(s), preferred exercise equipment, and results from their initial assessment. Participants will be educated on how equipment works and what exercises are appropriate, and will be guided on intensity levels. At the beginning of each session, vitals and pain will be assessed, and each participant will complete a minimum 5-minute warm-up. After the warm-up, each participant will complete cardiovascular training in bouts of at least 10 minutes. Staff will monitor the sessions to ensure that participants perform at least 30 minutes three times a week of moderate-to-vigorous exercise, as determined by a report of 12 or higher on the Borg's Rate of Perceived Exertion (RPE) Scale (6–20). Due to altered sympathetic innervation in PwSCI, target heart rate may not be reliable; therefore, RPE will be the real-time determinate of intensity. Activity monitors (GT9X Actigraph, Pensacola, FL) will be donned to capture intensity data to be processed post hoc. Each participant will then complete a 3–5-minute cool-down. After cardiovascular training, each participant will complete strength training geared toward their goals, with guidance from PQHWC staff

---

to perform a comprehensive variety of strength exercises to promote fat-free mass, muscle endurance, and overall strength. Staff will set up and monitor strength training to ensure that, for each exercise, participants perform at least two to three sets of 10–15 repetitions (reps) at 50%–75% one-rep max (1RM) for each exercise targeting functioning muscle groups. After strength training, participants will complete a 5–10 minute cool-down, and final heart rate, blood pressure, and pain will be assessed. Staff are occupational therapists and physical therapy assistants who have worked in an exercise setting with PwSCI. Staff will be taught the exercise guidelines and exercise session protocols using written materials, demonstration, and practice sessions. Following each exercise intervention session, participants will describe what they liked and did not like, provide a rating (1–5) of how much they gained from the session, and answer an open-ended item requesting suggestions for improvement. At the end of each session, the trainer will rate the participant's perceived participation during the session (1–6) using the Pittsburgh Rehabilitation Participation Scale.

The participants in the EEG will complete an intervention that consists of a one-on-one, hour-long educational session orienting participants to an online resource center, the National Center on Health, Physical Activity, and Disability (NCHPAD). NCHPAD promotes health and well-being for PwD through resources such as adapted exercise videos, information on accessible fitness equipment, personalized exercise videos tailored to PwD, and an individualized 14-week exercise program. Participants will be given an overview of NCHPAD and asked to identify resources of interest on the website. Each participant will be asked to use resources on NCHPAD to engage in physical activity for 12 weeks. Each participant will receive a weekly phone call to inquire about their physical activity, exercises engaged in, RPE during exercise, and whether any resources were used.

## ***E2 Subject Selection and Withdrawal***

### **2.a Inclusion Criteria**

- 1) Diagnosis of SCI
- 2) 18 years or older
- 3) Have written physician approval to participate in the study
- 4) Ability to use upper extremities to exercise
- 5) Participate in < 60 minutes of moderate-intensity exercise per week in the last month
- 7) Understand English at a sixth-grade level or higher
- 8) Be able to follow multi-step instructions
- 9) Independently provide informed consent
- 10) Willing to participate in three assessments and 36 intervention sessions

### **2.a Exclusion Criteria**

- 1) Enrollment in a structured exercise program in the past six months.
- 2) Have had cardiovascular complications within the past year
- 3) Currently receive medical treatment for an acute upper extremity injury
- 4) Have a Stage IV pressure injury
- 5) Have a cognitive impairment that does not allow them to provide consent or follow multi-step directions.

---

## **2.b Ethical Considerations**

Physical activity in healthy individuals and in people with varying pathologies is beneficial for physiological and psychological health and well-being, and these benefits are expected in people with SCI. Our previous studies have also shown that physical activity is safe and realistic for persons with SCI. There are no obvious ethical considerations.

## **2.c Subject Recruitment Plans and Consent Process**

Potential participants may either be approached or identified by the PI from Paraquad's waiting list, or potential participants may contact us after viewing a study flyer posted within community and rehabilitation facilities. The study coordinator may describe the study with participants over the telephone or in person and, if they are interested, verbal consent will be obtained to continue with the screening document. This process will be the same for all populations, as the randomization does not occur until after the first assessment is completed. After the screening document is complete, the study coordinator will obtain medical referrals from the participant's physician(s); once permission from the participant's physician(s) is received, the participant will be contacted via phone by the study coordinator and scheduled for their first assessment appointment. Prior to the scheduled initial assessment, a copy of the written consent form may be mailed to the potential participants so they may have time to review it, become familiar with it, and prepare any questions they may have. The study coordinator may also contact potential participants via phone 24–72 hours prior to their scheduled initial assessment to remind potential participants of their upcoming initial assessment appointment. Upon arriving to their first assessment appointment, a research staff member will review the written consent form with the potential participant. Potential participants will be given time to review the form additionally on their own, discuss with family members if they wish, and have any and all questions addressed. Potential participants will then be asked to initial, sign, and date the form, as necessary, prior to participating further in the initial assessment.

## **2.d Randomization Method and Blinding**

Randomization does not occur until after the initial assessment is completed. Immediately following completion of the initial assessment, each participant will be randomly assigned to either the CBEI ( $n = 20$ ) or EEG ( $n = 20$ ). To control for selection bias, stratified randomization will be used to ensure that the CBEI and EEG are balanced with respect to how long the participant has been injured ( $<2$  years or  $\geq 2$  years), the participant's level of injury (below C7 or C7 and above), age ( $<40$  years or  $\geq 40$  years of age), and gender. This will control for a large imbalance of participants allocated to one intervention. Research staff performing the assessments will be blinded to group randomization.

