## **G Statistical Plan**

### **G1 Sample Size Determination and Power**

This is a pilot study, with our primary interests in outcome variability and co-variability and estimates of feasibility and acceptability, which will aid in the planning of a larger trial. The sample size of 40 participants was selected to provide enough participants to assess the research protocol, determine trends in change, and provide data to calculate sample sizes for a larger RCT.

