### **G4 Statistical Methods**

*Aim 1:* Data will be collected and managed using Research Electronic Data Capture (REDCap) and exported to SPSS for analysis. Descriptive statistics will be used to describe the CBEI and the EEG. The data will be examined for normality, outliers, and errors. To examine whether the datasets meet the assumptions of normality, a Shapiro-Wilks test will be conducted. The assumptions of homogeneity of variance and homogeneity of covariance will be examined with Box's M and Mauchly's W tests, respectively. To examine the presence of outliers, histograms will be used. The purpose of the analysis is to compare the post VO2peak measures (primary outcome) between the two groups. First, a two sample t test (or non-parametric Wilcoxon test) will be used for unadjusted analyses. Then we will use a linear regression to compare VO2peak between the CBEI and EEG, adjusting for pre-VO2peak measures and other potential covariates. For other outcomes, based on the measurement scale, a similar analysis approach (unadjusted and adjusted) will be used. For binary outcomes, a Pearson Chi-square or fisher exact test will be used for unadjusted analyses, and a logistic regression model will be used for adjusted analyses. For continuous outcomes, we will perform

---

analyses similar to those of the VO2peak outcome. Additionally, effect size (d) associated with the intervention will be calculated using Cohen's *d* and will be interpreted as small (*d* ≤ .2), moderate (*d* ~ .5), or large (*d* ≥ .8). We will explore whether results differ depending on level of SCI and length of time living with an SCI. We will use dummy variables for these two variables and test the interaction term (intervention-by-the-dummy) in the model.

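### With 16 strata for 40 participants and no stated algorithm, balance cannot be ensured, and the analysis does not commit to adjusting for the four stratification factors

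*Combined protocol and SAP*

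**What the plan says.** Section E2, 2.d assigns participants one at a time: "Immediately following completion of the initial assessment, each participant will be randomly assigned". The planned arm sizes are 20 and 20. On the method it states that "stratified randomization will be used to ensure that the CBEI and EEG are balanced with respect to how long the participant has been injured" (under 2 years, or 2 years and over). It adds three more factors: injury level (C7 and above, or below C7), age (under 40, or 40 and over) and gender. On arm size it says: "This will control for a large imbalance of participants allocated to one intervention". Section E1 adds that a staff member outside assessment and delivery does the randomising. Neither section gives a block size, an allocation algorithm, a rule for sparse strata, or a way of reaching the 20/20 total.

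G4 begins the VO2peak comparison with an unadjusted two-sample test. It then fits a linear regression on the pre-intervention value "and other potential covariates", and does not say which of the two analyses is the main one. Injury level and time since injury reappear only in exploratory interaction models. Age and gender are not named in the analysis at all.

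**The concern.** Two things do not fit together.

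First, blocked lists balance the arms only when blocks are completed. With an average of 2.5 people per stratum, many blocks stay open at the end of recruitment, and a stratum with one person is a coin toss. The leftovers add up across strata, so the method as described does not support the word *ensure*.

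Second, the factors used to constrain the allocation are not committed to in the analysis. Stratifying on a factor that predicts the outcome makes the treatment estimate less variable. A model without that factor does not see the gain: it reports a standard error that is too large, and the chance imbalance that remains stays in the estimate. Open wording on covariates also lets the adjustment set be chosen after the data are seen. At stake are precision and prespecification, in a pilot whose estimates are meant to size a larger trial.

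**Working it through.** **Inputs from the protocol.** N = 40 (G1); 20 per arm, four factors, sequential assignment (2.d). Gender is taken as two levels because none are listed.

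**Number of strata.** 2 × 2 × 2 × 2 = 16. Mean stratum size 40/16 = 2.5, or 1.25 per arm. The plan gives no imbalance figure of its own to reproduce.

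**What such a scheme delivers.** Forty sequential participants were simulated (20,000 runs per scheme; 4,000 for minimisation). The documents give neither factor prevalences nor a block size, so both are assumed. The three prevalence sets were all factors at 50%; 25/50/60/25%; and 15/50/60/20%. On average 11 to 15 strata were occupied, and 3 to 4 held a single person. Ranges over the three sets:

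| Scheme | Exact 20/20 | 22/18 or worse | 24/16 or worse | Gap of 20+ points on some factor |
|---|---|---|---|---|
| Simple randomisation | 12–13% | 63% | 26–27% | 50–62% |
| Stratified, blocks of 2 | 28–31% | 23–28% | 0.4–1% | 1–2% |
| Stratified, blocks of 4 | 21–25% | 35–42% | 3–6% | 8–16% |
| Stratified, blocks of 6 | 18–22% | 42–51% | 6–12% | 15–33% |
| Minimisation, probability 0.8 | 54–57% | 4% | 0% | 8–10% |

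A repeat run for blocks of 2 or 4 gave 21 to 30% exact 20/20, and a 20-point gap in 2 to 3% and 11 to 16% of trials respectively.

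**What omitting the factors costs.** Let R² be the share of outcome variance that the factors explain beyond the other covariates. The documents do not give it; 20% and 40% are assumed. Simulation put the overstatement of the standard error at about 8 to 15%, with a type I error of about 2.5 to 3.8% against a nominal 5%. Adding the factors restored 5%.

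An approximation shows where this comes from. With all prevalences at 50%, a factor's imbalance between arms has the same variance as the arm-size difference. The SD of that difference was 6.35 under simple randomisation, 2.82 with blocks of 2 and 3.75 with blocks of 4. The fraction of factor imbalance that survives stratification is k:

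- blocks of 2: k = (2.82/6.35)² = 0.197
- blocks of 4: k = (3.75/6.35)² = 0.349

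True variance divided by the variance that the unadjusted model reports is 1 − R²(1 − k). The standard error is therefore overstated by the factor 1/√[1 − R²(1 − k)]:

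- blocks of 4, R² = 0.2: 1/√(1 − 0.2 × 0.651) = 1/√0.870 = 1.07
- blocks of 4, R² = 0.4: 1/√(1 − 0.4 × 0.651) = 1/√0.740 = 1.16
- blocks of 2, R² = 0.2: 1/√(1 − 0.2 × 0.803) = 1/√0.839 = 1.09
- blocks of 2, R² = 0.4: 1/√(1 − 0.4 × 0.803) = 1/√0.679 = 1.21

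So 8 to 15% is a fair central range, and the figure moves with the unstated block size.

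**What including them costs.** Intercept, arm and baseline leave 40 − 3 = 37 residual degrees of freedom; four main effects leave 33. If the factors predict nothing, the standard error widens by about 2%.

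**The case against.** The strongest reply is that the allocation scheme works rather well. A reader might infer from 2.5 people per stratum that stratification here fails to balance the factors and should be replaced. The figures do not support that. A 20-point gap on some factor falls from 50–62% under simple randomisation to 1–2% with blocks of 2 and 8–16% with blocks of 4. Minimisation, at 8–10%, is worse than the former and at best moderately better than the latter. Its clear advantage is in arm size only.

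A reader might also infer that 2.d promises an exact 20/20 split. It does not. The word *ensure* governs the four factors, while on arm size the claim is only about a large imbalance, and that aim is largely met with blocks of 2 or 4. Unequal arms also cost little. Efficiency relative to 20/20 is 4ab/N²: for 22/18, 4 × 22 × 18/1600 = 0.99; for 24/16, 4 × 24 × 16/1600 = 0.96.

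Further, this is a pilot without a power target: "The sample size of 40 participants was selected to provide enough participants to assess the research protocol". Chance imbalance is not bias, and adjustment for baseline VO2peak should absorb part of any effect of injury level or age. Extra covariates use degrees of freedom, and fewer are available once G5 restricts the analysis to complete data.

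All of this stands, and it limits the point. It does not answer two things: *ensure* is stronger than the method, and the analysis leaves open whether the randomisation factors are used at all.

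**Conclusion.** The point holds as a gap in specification and analysis. It does not show that the design fails. Sixteen strata for 40 people, with no algorithm stated, cannot ensure factor balance and will usually miss an exact 20/20 split (about 21 to 31% exact with assumed blocks of 2 or 4). Even so, the scheme balances far better than simple randomisation, and 24/16 or worse occurs in at most about 6% of trials at those block sizes.

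The more useful part concerns G4. Without a commitment to the four factors, the standard error is overstated by about 8 to 15% if they explain 20 to 40% of the variance beyond the other covariates, and not at all if they explain none. The error is conservative: it makes the comparison less sensitive and does not create false positives. It would be wrong to conclude that the treatment comparison is biased. The sizes rest on assumed prevalences, block sizes and variance explained, none of which the documents give.

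**What to change.** In G4, name the adjusted regression as the main VO2peak analysis. Prespecify its covariates: baseline VO2peak, time since injury, injury level, age group and gender, as main effects in the categories used for randomisation. Do the same for the other continuous outcomes, each with its own baseline value. Keep the unadjusted test as supportive.

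In 2.d, state the allocation algorithm, including block sizes if blocks are used, and replace ensure with promote. Very small fixed blocks balance best but make later assignments within a stratum easier to predict, so the choice should be explicit. Minimisation on the same factors with a random element is an option that would bring arm sizes closer to 20/20; it is not a required change.

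The cost is a few sentences of text and four degrees of freedom, about a 2% wider standard error in the worst case where the factors predict nothing.
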